3.4 Part A Dose Escalation Schedule and Treatment Schema

Oral PCLX-001 will be provided as continuous daily dosing on a 28-day cycle. The starting dose of PCLX-001 will be 20 mg daily (Section 3.1.1). Dose escalation will follow a modified Fibonacci design such that the magnitude of escalation decreases as the dose level nears the human equivalent dose (HED) of the HNSTD in dogs and then escalate at 1.4 times the previous dose until MTD or RP2D is reached.

The dose level schedule is as below (1 cycle = 28 days):

Dose Level**	Daily Oral Dose (mg)	Number of Capsules	
		10 mg	70 mg
-1	10	1	0
1 (starting dose)*	20	2	0
2	40	4	0
3	70	0	1
4	100	3	1
5	140	0	2
6	210	0	3
7	280***	0	4

* Trial will start at Dose Level 1 and will de-escalate to Dose Level -1 if DLT is observed.

** If ≥ 2 out of 6 DLTs are observed in Dose Level -1, 1 or 2 then consideration will be given to changing dosing schedule (eg. 28-day schedule with each week comprising 4 days on medication and 3 days off medication).

*** If DLT is not observed at the dose of 280 mg, the dose will be considered the MTD. If required, the MTD cohort may be expanded by an additional 10 patients for further toxicity and response assessment.

For each dose-escalation cohort, treatment with the first dose of PCLX-001 will be staggered such that the second participant enrolled in the cohort will receive PCLX-001 at least two weeks after the first participant and all subsequent participants at least one week after the previous participant.

Each participant will be treated with the dose of PCLX-001 they are assigned to, until the occurrence of a DLT or other study stopping point occurs, at which point the dose of PCLX-001 will be modified as per protocol or study drug administration will be discontinued.

If DLT occurs at Dose Level 1, a safety meeting will occur to determine the feasibility of continuing the study at Dose Level -1. Alternative dose schedules may also be considered if DLTs occur during Dose Levels, -1, 1 or 2.

Participants who experience a DLT or have received at least 21 days of PCLX-001 during cycle 1 will be evaluable for toxicity. If a participant does not meet these criteria, the participant may be replaced (Section 4.3).

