3.6 Treatment Duration and Discontinuation

In the absence of treatment delays due to adverse events, treatment may continue unless the following reasons to discontinue PCLX-001 occur:

- Disease progression
- Intercurrent illness preventing further administration of treatment
- Unacceptable adverse event(s)
- Patient withdrawal from study (patient choice)
- Treating physician choice
- Delay in subsequent cycles of chemotherapy of longer than 28 days due to toxicity
- Failure of patient to adhere to study requirements

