5.3.1 Cycle 1 DLT Modifications for Part A Dose-Escalation Cohorts

If a patient experiences a treatment related hematological or non-hematological DLT (as defined in Section 3.2) during Cycle 1, the next dose of PCLX-001 will be delayed for up to 28 days for Part A. If the toxicity fails to resolve to CTCAE Grade ≤ 2 within 28 days, the patient should be withdrawn from study treatment but followed for safety until resolution.

If the toxicity resolves to CTCAE Grade ≤ 2 , re-treatment with PCLX-001 can be considered. Re-treatment of this patient should be at 1 dose level below the initial dose. Detailed dose modifications are described in Table 5-1. Patients experiencing any drug-related, clinically significant, non-hematological CTCAE Grade 4 toxicity will be withdrawn from study treatment but followed for safety until resolution. There will be no intrapatient dose escalation and no more than two dose reductions will be allowed.

Table 5-1: Dose Modifications of PCLX-001

Existing Dose (mg)	Modified Dose (mg)
280	210
210	140
140	100
100	70
70	40
40	20
20	10
10	Discontinue study drug

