5.3.2 Dose Modifications for HEMATOLOGIC Toxicities

For cycle 2 and beyond, Day 1 administration of PCLX-001 requires a platelet count of $\geq 75 \times 10^9/L$ and an absolute neutrophil count (ANC) of $\geq 1.5 \times 10^9/L$. CBC's drawn within 72 hours of treatment day may be used provided they meet parameters. However, if treatment parameters are not met, dose interruption will be made on the basis of blood counts taken the day of scheduled treatment. If counts are below this threshold, treatment will be delayed for 1 week and reassessed weekly until these parameters are met.

If a patient experiences a hematologic DLT in the preceding cycle OR if treatment is held for > 7 days due to neutropenia and/or thrombocytopenia, then the subsequent cycle will be administered at one lower dosing level. No more than two dose reductions will be allowed.

Patients should not receive prophylactic G-CSF for cycle 1. Subsequent use will be at the discretion of the treating physician and as per the ASCO guidelines on colony stimulating factors.

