5.3.3 Dose Modifications for NON-HEMATOLOGIC Toxicities

For a Grade ≥ 3 non-hematological toxicity considered to be clinically significant and attributed to PCLX-001, treatment will be delayed for up to a maximum of 28 days. If the toxicity resolves to CTCAE Grade ≤ 2 , the next dose of PCLX-001 can be considered at 1 lower dose level (Table 5-2). Grade 4 clinically significant toxicities related to PCLX-001 will result in discontinuation of PCLX-001.

There will be no intrapatient dose escalation and no more than two dose reductions will be allowed.

Table 5–2: Non-hematological Criteria for Dose Delay and Dose Modification

CTCAE	Dose delay	Dose modification
Grade^a		
0 – 2	Treat on time	No change
3	Delay ^b until CTCAE Grade ≤2	Decrease 1 dose level ^c
4	Discontinue permanently	Discontinue permanently

^a Excludes alopecia, non-refractory nausea/vomiting, and non-refractory diarrhea. For TLS see Table 5-3

^b If no recovery after 28-day delay, PCLX-001 treatment will be discontinued.

^c Dose will not be re-escalated after reduction for toxicity. If more than 2 dose reductions are required, treatment will be discontinued.

Gastrointestinal Events

Diarrhea: No prophylactic treatment for diarrhea is recommended. Anti-diarrheals can be used when needed. A further dose of study medication should not be given before treatment related diarrhea has recovered to CTCAE Grade ≤ 2.

Nausea/Vomiting: No prophylactic treatments for nausea or vomiting are recommended, but anti-emetic drugs can be used when needed. A further dose of study medication should not be given before treatment related nausea/vomiting has recovered to CTCAE Grade ≤2.

Constipation: Patients can continue laxative as concomitant medication, but start of prophylactic treatments before study drug is administered is not recommended. Laxative can be used when needed.

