- b. If a patient discontinues study treatment at any time during the study for any reason (except for patients who died, withdrew consent and objected to further data collection, or were lost to FU), an active FU assessment should be performed 30 days (± 4 days) after the last dose of the last study drug.
- c. Prescribed and OTC.
- d. Questioning for AEs will be conducted at clinic visits; in addition, spontaneous reports of AEs will be collected throughout the study.
- e. PK sampling: For patients in dose escalation, see Table 7C for schedule. For patients in dose expansion, see Table 7D for schedule.
- f. To be taken pre-dose of each cycle Day 1 within 60 min before the morning dose and EOT
- g. Hematology includes CBC + differential (i.e. hemoglobin erythrocytes, leukocytes, platelets, MCV, RDW, hematocrit, neutrophils, lymphocytes, monocytes, eosinophils, basophils, immature granulocytes, nucleated RBCs). Detection of CTCAE Grade 4 neutropenia (only Cycle 1) will trigger twice-weekly white blood cell counts to be performed, so that DLT determination can be made.
- h. Blood chemistry includes: sodium, potassium, chloride, bicarbonate or total CO² (as per site practice), calcium, phosphate, magnesium, total protein, albumin, glucose, serum creatinine, urea, uric acid, total bilirubin, ALT, AST, LDH, alkaline phosphatase, lipase.
- i. Window for tumour assessment is ± 5 days from Day 28 of the even-numbered cycles. CT of the relevant disease region for solid tumors and CT thorax, abdomen, pelvis \pm neck for NHL.
- j. Women of childbearing potential (including women of childbearing potential whose partners are sterilized) must have a negative pregnancy test.
- k. This scan should only be performed for NHL patients and is optional (i.e. not required for patients with other histologies). If a PET-CT is performed at screening, it should be repeated once after the sixth cycle if no progressive disease is detected during the course of treatment and / or to confirm complete response or disease progression.
- l. Exam to be symptom-directed.
- m. To be performed if clinically indicated (e.g. positive HBsAg and/or anti-HCV tests as performed during screening).
- n. Unless otherwise indicated, the window for visits is ± 2 days.
- o. Electronic records will be used to assess patient survival monthly (± 1 week) from the date of the follow-up visit.

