7.3 Determination of Efficacy Outcomes

Tumor response and progression of solid tumors and NHL will be evaluated by the investigator at each study center consistent with RECIST 1.1 criteria (see [Appendix B](#)), or Lugano Classification of Lymphoma response (see [Appendix C](#)).

Tumor markers can play a role in detecting disease and assessing response to therapy in selected groups of patients. In monitoring patients for disease progression, tumor marker levels should be determined according to clinical practice (e.g., CA125 for ovarian cancer, CEA for colorectal cancer, PSA for prostate cancer).

Solid Tumors

In *measurable* lesions (i.e. at the primary site, visceral [≥ 1.0 cm long axis], or nodal [in lymph nodes ≥ 1.5 cm short axis] lesions), the objective response will be assessed by contrast-enhanced CT or MRI and documented consistent with RECIST 1.1 criteria (see [Appendix B](#)). Tumor measurements for efficacy evaluation will be made every 2 cycles, beginning with a baseline scan and unless progression is noted, all lesions will be assessed and reported at the end of every second cycle, starting at the end of Cycle 2.

Non-Hodgkin's Lymphoma

Efficacy will be assessed based on radiological tumor evaluations, which will include neck, chest, abdomen, and pelvis by contrast-enhanced CT / MRI scans. PET-CT can be utilized throughout the study if it is considered standard of care at the institution. Scans will be performed as shown in Table 7A and Table 7B and will be evaluated locally at the study site.

PET-CT is optional in this study and should be done based on institutional standards whereas the CT portion of the PET-CT should be of diagnostic quality, i.e. appropriate radiation dose and contrast enhancement. In case the CT portion of the PET-CT is performed for attenuation correction only an additional whole body CT in diagnostic quality is needed. If a PET-CT with a PET positive finding was performed at screening an interim PET-CT should be done after the sixth cycle. For any imaging follow-up after interim PET-CT it is recommended to confirm any changes in previous metabolic overall response that were assessed with CT alone with PET-CT.

Response assessment will be based on the Lugano Classification (see [Appendix C](#)).

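### Tumour scans are counted in cycles, so a toxicity delay can move the first scan from Day 56 to as late as Day 84 and make entry to the efficacy set depend on tolerability

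*Combined protocol and SAP*

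**What the plan says.** Both scan rules count in cycles. Table 7B note i (7.1) gives a window of 5 days either side of its anchor: "days from Day 28 of the even-numbered cycles". Section 7.3 says "Tumor measurements for efficacy evaluation will be made every 2 cycles, beginning with a baseline scan", and then "all lesions will be assessed and reported at the end of every second cycle, starting at the end of Cycle 2". Section 3.4 fixes the nominal cycle: "Oral PCLX-001 will be provided as continuous daily dosing on a 28-day cycle". Tumour markers in Table 7B follow the same every-second-cycle entry.

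The start of a cycle can move:

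- **5.3.2 (low counts, Cycle 2 onward):** "treatment will be delayed for 1 week and reassessed weekly until these parameters are met".
- **5.3.3 (non-hematologic toxicity, Grade 3 or worse):** "treatment will be delayed for up to a maximum of 28 days".
- **5.3.1 (Cycle 1 DLT):** "the next dose of PCLX-001 will be delayed for up to 28 days for Part A".
- **3.6 (reason to stop treatment):** "Delay in subsequent cycles of chemotherapy of longer than 28 days due to toxicity".

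On use of the scans, Table 8-1 (8.2) limits the efficacy population to treated participants with at least one on-treatment tumour assessment. The tumour assessment row of Table 7B carries no mark at the end-of-treatment visit. Section 3.5 lists ORR among the inputs to the RP2D. Section 4.3 allows further enrolment to keep 20 patients evaluable for response if dropout in an expansion cohort reaches 20%.

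**The concern.** When scans follow cycle number and cycle starts follow recovery from toxicity, the date on which response or progression is assessed depends on how well the patient tolerates the drug. If toxicity delays become more frequent as dose rises, which is likely but is not a figure the documents give, assessment timing also varies with dose.

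Three results are exposed:

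- **The evaluable set.** A patient with a delayed first scan has longer in which to stop before being scanned. One who does stop is left out of the efficacy population instead of counting as a non-responder. The extra enrolment in 4.3 restores the number evaluable but not the patients who were selected out.
- **ORR.** Its denominator is that set, and it feeds the RP2D decision.
- **The timing of progression calls.** Progression is a reason to stop treatment under 3.6, and it is looked for on different dates in delayed and undelayed patients.

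**Working it through.** The plan gives no figure of its own here to reproduce. The check is date arithmetic plus one illustration.

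**Inputs.** Cycle length 28 days (3.4). Scan on Day 28 of even cycles, ± 5 days (Table 7B note i). Let d2, d3 and d4 be the delays of Day 1 of Cycles 2, 3 and 4, each 0 to 28 days (5.3.1 to 5.3.3, limit from 3.6).

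**First scan.** Day = 28 + d2 + 28 = 56 + d2.

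| Delay of Cycle 2 Day 1 | First scan due | Window |
|---|---|---|
| 0 | Day 56 | 51-61 |
| 7 | Day 63 | 58-68 |
| 14 | Day 70 | 65-75 |
| 21 | Day 77 | 72-82 |
| 28 | Day 84 | 79-89 |

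A one-week delay already puts the due date outside the undelayed window. From 14 days the two windows do not overlap.

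**Second scan.** Gap from scan 1 = 56 + d3 + d4. With no delay it is 56 days; with 7 + 7 it is 70; with 28 + 28 it is 112. Using both windows, the last case runs from 102 to 122 days.

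**When progression is seen.** Compare scans on Days 56, 112, ... with scans on Days 84, 140, ... after a 28-day delay of Cycle 2.

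- Progression on Day 40 is seen on Day 56 (fixed) or Day 84 (delayed).
- Progression on Day 60 is seen on Day 112 (fixed) or Day 84 (delayed).
- If progression is assumed uniform over the first 84 days, the mean lag is 84/2 = 42 days on the delayed schedule. On the fixed schedule it is (56/84) × 28 + (28/84) × 42 = 32.7 days. The difference is about 9 days on average, but the sign varies by patient.

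**Stopping before the first scan (illustration).** The documents give no stopping rate. Assume a constant rate h of 0.10 to 0.20 per month of 30.4 days, so that P(stop before day t) = 1 - exp(-h × t / 30.4).

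| h per month | t = 56 | t = 84 | Rise |
|---|---|---|---|
| 0.10 | 16.8% | 24.1% | 7.3 points |
| 0.20 | 30.8% | 42.5% | 11.7 points |

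These are counted from first dose and apply to a patient delayed the full 28 days. The cohort effect scales with the share delayed. If a quarter of patients were delayed that long (also an assumption), the rise would be 0.25 × 7.3 = 1.8 to 0.25 × 11.7 = 2.9 points, or about 0.4 to 0.6 of a patient in a cohort of 20.

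**The case against.** The best defence is that counting in cycles equalises nominal exposure. A patient delayed 28 days before Cycle 2 is scanned on Day 84 after the same two nominal cycles as an undelayed patient on Day 56. Under calendar scanning that patient would first be imaged after about 28 days of drug. This stands as a real cost of the fix. It is limited, because a delayed patient who stays on study is scanned again 56 days later, and it can be handled by reporting exposure.

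The other side can also say that activity is a preliminary secondary objective, that the statistical section is descriptive, and that no PFS, time-to-progression or response-duration endpoint is defined. That is correct, and it confines the effect to ORR, the evaluable set and the timing of progression calls. Unscheduled visits (7.2) and PET-CT in lymphoma where it is standard of care (7.3) offer some flexibility, but neither fixes a scan date.

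A reader might infer four stronger things that the documents do not support:

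- **That two holds push the first scan to Day 112.** Only one cycle boundary precedes it. A second slip would need a mid-cycle hold to lengthen the cycle; the protocol does not say that it does, and 5.2 says missed doses are not made up. The 112-day figure belongs to the gap between scans 1 and 2.
- **That patients stay on drug longer.** The added time is largely time off drug.
- **That progression is always found later.** The Day 60 example runs the other way.
- **That dose levels or cohorts cannot be compared at all.** No formal comparison is planned, and Cohorts A and B are different diseases.

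**Conclusion.** The point holds as a modest, inexpensive defect. As written, the first scan can slip by up to 28 days (Day 56 to Day 84, or 89 with the window), and the second interval can double from 56 to 112 days. Both slips are driven by toxicity. The fault is an unequal assessment clock, not uniformly late detection. Its main consequence is that delayed patients who stop early can fall out of the ORR denominator.

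The date arithmetic rests on the text alone, read as applying to delays of a cycle's Day 1. Two things are assumed: the monthly stopping rate behind the 17%-31% and 24%-43% figures, and a rise of toxicity delays with dose. The share of patients who will be delayed is unknown, so the size of any bias in ORR cannot be derived from the documents.

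**What to change.** In 7.3 and Table 7B note i, schedule tumour assessments and the paired tumour markers every 56 ± 5 days counted from Cycle 1 Day 1, regardless of dose holds or cycle delays. The first scan then falls on Day 56 (window 51 to 61) for every patient still on study. Two clarifications belong with it: a scan taken during a hold counts as on-treatment for Table 8-1, and the protocol should say whether a mid-cycle hold changes the counting of cycle days.

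The change is to wording only. Patients without delays keep the same scans on the same days, and no dose or treatment rule is touched. There are two costs. Some scans will fall outside dosing visits. Delayed patients will be first imaged after less drug, so cumulative exposure to the scan date should be reported alongside each response.

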3.2 Definition of Dose Limiting Toxicity and Maximum Tolerated Dose

Toxicities are to be graded according to the National Cancer Institute Common Terminology Criteria for Adverse Events (NCI CTCAE, Version 5.0). A copy of the CTCAE version 5.0 can be downloaded from the CTEP home page (<http://ctep.cancer.gov>).

Dose Limiting Toxicity (DLT) for Part A, dose-escalation, is defined as any of the following AEs related to PCLX-001 treatment occurring in Cycle 1:

Hematologic

- Grade 4 thrombocytopenia (platelet count < 25 x 10⁹/L)
- Grade ≥ 3 thrombocytopenia (platelet count < 50 x 10⁹/L) associated with any major bleeding, and/or requirement for transfusion
- Grade 4 neutropenia (ANC < 0.5 x 10⁹/L) for ≥ 7 days^a
- Febrile neutropenia. (Per NCI CTCAE, ANC < 1.0 x 10⁹/L and fever ≥ 38.3°C or a

sustained temperature of $\geq 38^{\circ}\text{C}$ for more than one hour). Febrile neutropenia is by definition a grade ≥ 3 toxicity.

^a Detection of CTCAE Grade 4 neutropenia (only in Cycle 1) will trigger twice-weekly white blood cell counts to be performed, and will be considered a DLT if drug interruption lasts ≥ 7 days.

Non-hematologic

Any non-hematological toxicity of CTCAE Grade ≥ 3 is considered a DLT, excluding the following:

- Grade ≥ 3 nausea, vomiting and diarrhea which are controlled with anti-emetics and/or other supportive care within $\leq 72\text{hr}$
- Brief (i.e. lasting ≤ 72 hours) CTCAE Grade 3 fatigue
- Alopecia of any grade
- Isolated, asymptomatic, biochemical laboratory values including electrolyte abnormalities, above or below normal reference ranges, which are judged not clinically significant by the Investigator
- Miscellaneous
- Any patient meeting Hy's law of drug-induced hepatic injury (AST or ALT >3 times ULN with bilirubin 2 times ULN; absence of initial cholestasis with ALP >2 times ULN; no other explanation) is considered a DLT.
- Any toxicity thought to be related to study drug that, at the discretion of the investigator, or his/her designated associate(s), is thought to warrant withholding the drug may be declared as a DLT. Such toxicities might for example be CTCAE Grade 1 or CTCAE Grade 2 toxicities that interfere with the activities of daily life, such as long-lasting fatigue, or anorexia, making a dose reduction necessary in order to ensure the patient's compliance.

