Table 7B: Schedule of Evaluations (Study Flow Chart) – TREATMENT AND FOLLOW-UP

Measures / actions	Treatment ⁿ								FU	
	Cycle 1					Cycle 2		Cycle ≥ 3	EOT visit	Safety FU visit ^b
	D1 ^a	D2	D8	D15	D22	D1	D15	D1		Long-Term FU ^o
Before study drug administration										
Check of inclusion / exclusion criteria	X									
Abbreviated medical history	X		X	X	X	X	X	X	X	
Concomitant medications ^c	X		X	X	X	X		X	X	
Assessment of toxicities (AEs) ^d	X		X	X	X	X	X	X	X	
12-lead ECG (standard, triplicate)	X					X			X	X
Blood pressure, heart rate, & body temperature	X		X	X	X	X	X	X	X	
Physical examination ^l	X		X	X	X	X		X	X	X
Body weight	X		X	X	X	X	X	X	X	X
ECOG performance status assessment	X		X	X	X	X	X	X	X	X
Blood sample collection for biomarker analysis ^f	X					X		X	X	
Blood / urine sample collection for laboratory safety assessments										
• Hematology ^g	X		X	X	X	X	X	X	X	
• Blood chemistry ^h	X		X	X	X	X	X	X	X	
• Calculation of eGFR by Cockroft-Gault	X					X				
• Coagulation (aPTT; PT/INR)	X					X				
• Thyroid function (TSH and T ₄ [total or free per local standard])	X					X			X	
• Virology (HBV DNA, HCV RNA) ^m	X									
• Pregnancy test (serum or urine) ^j	X									
• Urinalysis (dipstick)	X			X		X			X	
Tumor assessment all tumors (CT or MRI) ⁱ							End of every second cycle			
PET-CT (optional, NHL patients only) ^k							Once after sixth cycle			
Blood sample collection for tumor marker, if applicable (e.g., CA125, CEA, PSA)							End of every second cycle			
Survival status										X ^o

Table 7B: Schedule of Evaluations (Study Flow Chart) – TREATMENT AND FOLLOW-UP (continued)

Measures / actions	Treatment								FU
	Cycle 1					Cycle 2		Cycle \geq 3	
	D1 ^a	D2	D8	D15	D22	D1	D15	D1	
Study drug administration									
Review of patient study medication diary and compliance of medication taken at home	X	X	X	X	X	X	X	X	
PCLX-001 administration at study center	X	X	X	X	X	X	X	X	
Before & after study drug administration									
PK sampling (plasma) for PCLX-001 ^e escalation	X	X	X	X	X	X	X	X	
PK sampling (plasma) for PCLX-001 ^e expansion	X			X		X		X	

- a. Any of the assessments scheduled before drug administration on C1D1 may be missed without protocol deviation if the same assessment has been obtained and reviewed within 3 days before the start of treatment (except PK and exploratory biomarker analysis).

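### The ±2-day visit window allows Part A Cycle 1 blood counts up to 11 days apart, so a Grade 4 neutropenia of 7 to under 11 days that starts and resolves between visits can go undetected

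*Combined protocol and SAP*

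**What the plan says.** **Schedule.** Table 7B (Section 7.1) places Cycle 1 hematology on Days 1, 8, 15 and 22, and the next count on Cycle 2 Day 1 (nominal Day 29). None is due on Day 2. Note n gives the default: "Unless otherwise indicated, the window for visits is" ±2 days. Table 7C repeats ±2 days for Days 8, 15 and 22 and Cycle 2 Day 1. Under note a, the Day 1 count may be skipped "if the same assessment has been obtained and reviewed within 3 days before the start of treatment".

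**DLT.** The hematologic list in Section 3.2 includes "Grade 4 neutropenia (ANC < 0.5 x 10⁹/L) for ≥ 7 days". Footnote a to that bullet says that a Grade 4 value found during the first cycle "will trigger twice-weekly white blood cell counts to be performed, and will be considered a DLT if drug interruption lasts ≥ 7 days".

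**Trigger.** Table 7B note g repeats the twice-weekly counts and gives their purpose: "so that DLT determination can be made". In both places the extra counts depend on a Grade 4 value having already been found.

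**What is absent.** No section sets a maximum interval between Cycle 1 counts. Unscheduled visits (Section 7.2) are left to the investigator's discretion.

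**The concern.** Counts exactly 7 days apart must meet any Grade 4 episode of 7 days or more at least once. A window that moves each visit independently removes that guarantee, because one early visit followed by one late visit leaves a gap longer than the episode. The twice-weekly counts cannot repair this, since an unseen episode never starts them.

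Marrow toxicity is expected with this drug: Section 1.2.4 attributes dose-limiting toxicity in rats and dogs partly to reduced hematopoiesis. Cycle 1 DLTs drive escalation and the MTD (Sections 3.2 and 3.3). A patient with an unseen episode has still attended the scheduled evaluations, so would normally enter the MTD-determining population (Table 8-1) as DLT-free. That patient could also go up to 11 days with a Grade 4 count and no sample.

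**Working it through.** The protocol states no maximum gap and no detection rate, so there is no figure of its own to reproduce.

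**1. Largest compliant gap.** Gap = (later nominal day + 2) − (earlier nominal day − 2), with Day 1 fixed at first dose.

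| Pair of counts | Extreme compliant days | Gap |
|---|---|---|
| Day 1 to Day 8 | 1 and 10 | 9 |
| Day 8 to Day 15 | 6 and 17 | 11 |
| Day 15 to Day 22 | 13 and 24 | 11 |
| Day 22 to Cycle 2 Day 1 | 20 and 31 | 11 |

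If the window is read as running from the previous visit, the maximum is 7 + 2 = 9 days, still above 7. If the Day 1 count is taken 3 days early, the count-to-count gap to Day 10 is 12 days, of which 9 are on drug.

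**2. What can be missed.** An episode of L days fits inside a gap G if L < G. Only episodes of 7 to under 11 days both meet the duration in the bullet and can escape every scheduled count. Example: counts on Days 6 and 17, Grade 4 from Day 8 to Day 15.

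**3. How often, under stated assumptions.** Assume that visit shifts u are independent and uniform on −2, −1, 0, +1, +2, that onset is uniform, and that the episode has fixed length and resolves by itself. Then G = 7 + (u₂ − u₁) and E[G] = 7. Of the 25 combinations, gaps of 8, 9, 10 and 11 days arise in 4, 3, 2 and 1. So 10/25 = 40% of adjacent windowed pairs exceed 7 days, and 1/25 = 4% reach 11.

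P(missed) = E[max(G − L, 0)] / E[G]:

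- L = 7: (4×1 + 3×2 + 2×3 + 1×4)/25 = 0.80; 0.80/7 = 11%
- L = 8: (3×1 + 2×2 + 1×3)/25 = 0.40; 0.40/7 = 6%
- L = 9: (2×1 + 1×2)/25 = 0.16; 0.16/7 = 2%
- L = 10: 1/25 = 0.04; 0.04/7 = 0.6%

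A simulation with onset restricted to Days 1 to 22 gives 12%, 6%, 2% and 0.6%. Within a single 11-day gap, the missed share of 7-day episodes is (11 − 7)/11 = 36%. On the exact nominal schedule it is 0%.

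**4. Does detection lead to classification?** Suppose that duration is counted from the first Grade 4 sample, with perfect follow-up afterwards. This is an assumption, because the protocol gives no counting rule. An episode of L days is then documented as 7 days or more only if the first sample falls within L − 7 days of onset. The shortest compliant gap between windowed visits is 7 − 4 = 3 days. For L up to 10 the chance is therefore (L − 7)/7, both with exact weekly spacing and with the ±2-day window:

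- L = 7: 0%
- L = 8: 14%
- L = 9: 29%
- L = 10: 43%

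On that way of counting, closing the gap changes detection but not how these episodes are classified.

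**The case against.** A reader might infer that about one in nine true neutropenia DLTs is lost and that the MTD is biased upward to match. The documents do not support this, for four reasons.

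- **The DLT definition is not settled.** Under footnote a the DLT depends on drug interruption. An unseen episode causes none, so it is not a DLT under that wording. It is one only under the bullet. This contradiction is more basic than the window.
- **Detection is not classification.** As step 4 shows, a 7-day cap alone need not turn a missed episode into a counted DLT. It could do so under a more inclusive rule, such as counting back to the last sample that was not Grade 4.
- **The episode must resolve on treatment.** Dosing is continuous and daily (Section 3.4), and an undetected patient is not interrupted. Neutropenia that persists is seen at the next count.
- **No event rate is given.** The 11% is conditional on a qualifying episode, so it says nothing by itself about the MTD.

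There are also partial safeguards. Febrile neutropenia is a separate DLT, and investigators may declare DLTs (Section 3.2). Unscheduled visits are allowed. Cycle 2 Day 1 requires an ANC of at least 1.5 × 10⁹/L (Section 5.3.2). Each patient's Cycle 1 hematology goes to safety cohort review (Section 11.2). None of these produces a count in an afebrile patient without symptoms between visits, so the detection gap remains, in a narrow range of episodes.

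**Conclusion.** The calendar point holds. Compliant Part A Cycle 1 counts can be 11 days apart (9 from Day 1), and an afebrile Grade 4 neutropenia of 7 to under 11 days that begins and ends between two of them can go unseen and never trigger closer monitoring. The miss rates of about 11%, 6% and 2% for 7-, 8- and 9-day episodes rest on assumed uniform visit days and onset and on self-resolving episodes. They fall if sites keep near the nominal days or if neutropenia persists under dosing. When a miss does cost a DLT, the error can only favor escalation, but neither its frequency nor its effect on the MTD can be derived from the protocol. Severity: minor.

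**What to change.** 1. Add to Table 7B note g or n: in Part A Cycle 1, hematology samples are taken no more than 7 days apart from first dose through Cycle 2 Day 1. A blood count alone satisfies this; the rest of the visit keeps its ±2 days. Counting from first dose matters because note a allows an early Day 1 sample.
2. State that a late sample alone does not make a patient non-evaluable. Otherwise Table 8-1 (scheduled safety evaluations undergone) and Section 4.3 (replacement for non-compliance) could be read to remove the patient.
3. Reconcile the Section 3.2 bullet (duration of ANC below 0.5 × 10⁹/L) with footnote a (drug interruption of 7 days or more), and state how duration is counted when onset falls between samples. Without this, item 1 secures detection only. The triggered test is named as a white blood cell count while the bullet is defined on ANC; align these in the same edit.

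**Cost.** The late half of the window is lost for four blood counts: samples are due by Days 8, 15, 22 and 29 at the latest. The cap is compatible with the existing windows. A patient first sampled on Day 6 can follow on Days 13, 20 and 27, all compliant, and Section 5.3.2 already accepts a count within 72 hours of the treatment day. No extra draws are needed if the weekly rhythm is kept.
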